3 OBJECTIVES AND ENDPOINTS

OBJECTIVES	ENDPOINTS	JUSTIFICATION FOR ENDPOINTS
Primary		
The primary objective of this study is to understand the pulmonary immune response to mycobacterial antigens by determining the persistence of antigen-specific immune cells in the airways versus circulation after local bronchoscopic instillation of PPD into the lungs of adults with or without LTBI.	The primary endpoint will be the enumeration of Mtb antigen-specific CD4+ and CD8+ T cell populations in the airway and peripheral blood at early and late time points after bronchoscopic PPD instillation.	This endpoint is chosen to determine the point after directed bronchoscopic exposure to Mtb peptide the antigen-specific T cell response is strongest both locally in the lung and systemically in the blood.
Secondary		
The secondary objective is to characterize the location and persistence of immune cell activity in the pulmonary parenchyma and thoracic lymph nodes with positron emission tomography combined with chest computed tomography (PET-CT) after bronchoscopic PPD instillation in adults with or without LTBI.	The secondary study endpoint of this study is the quantification of FDG SUV throughout all lung fields and mediastinal lymph nodes of LTBI and non-LTBI patients at days -7, +4, and +20 after PPD bronchoscopic instillation.	This endpoint is chosen in order to identify and track over time the geographically anatomic distribution of immune cell activity in the lungs after PPD instillation.
Exploratory		
The exploratory objectives of this study are (a) to perform phenotypic and functional analysis of immune cell populations in the airways vs circulation following bronchoscopic instillation of PPD into the lungs of individuals with or without LTBI, (b) to characterize the production of soluble mediators (i.e. cytokines, lipid mediators, defensins) in BAL	(a) An exploratory endpoint will be the quantification of frequencies of cell surface molecules, intracellular cytokines and transcription factors among immune cell populations in the airways vs circulation following bronchoscopic instillation of PPD into the lungs of individuals with or without LTBI. (b) An exploratory endpoint will involve the	These endpoints are chosen to characterize the cellular phenotype and function of the most influential immune cell populations within the context of pulmonary tuberculosis in the local lung micro-

OBJECTIVES	ENDPOINTS	JUSTIFICATION FOR ENDPOINTS
fluid vs blood within the same context.	identification and quantification of soluble mediators in the airway and peripheral blood after PPD instillation in the lungs within the same context.	environment as compared to systemically at empirically selected early and late time points post Mtb antigen exposure.

4 STUDY DESIGN

4.1 OVERALL DESIGN

Hypothesis

The major hypothesis of this single-site pilot study is that recruitment of antigen-specific T cells and innate immune cell subsets following bronchoscopic instillation of purified protein derivative (PPD) from *M. tuberculosis* into the lung will occur primarily in individuals with latent TB infection. These Mtb-specific T cell responses will occur only in the segments into which PPD was instilled and not in the control lung segments. Lastly, pulmonary immune cell activation and number will peak early after PPD instillation and subsequently wane both in the airways and peripheral blood. These responses will be much more pronounced in the local pulmonary micro-environment as opposed to the systemic vasculature.

Using PET-CT imaging after PPD instillation, we hypothesize that it will be possible to identify increased cellular activity in draining thoracic lymph nodes, as well as in the pulmonary parenchyma. Furthermore, we expect that the above signals we are able to discern will progressively wane in the weeks following bronchoscopic PPD instillation.

Longitudinal Study Design

We plan to screen up to 100 non-LTBI controls vs confirmed LTBI to enroll up to 25 individuals in order to have a total of 20 individuals who are concordant on the PPD and IGRA test complete the study as follows:

Group A (LTBI Group): 13 PPD + and IGRA + subjects

[figure not shown]
Group B (non-LTBI Group): 7 PPD - and IGRA - subjects

We seek to enroll individuals at a 2:1 ratio of Group A:Group B in order to maximize the data derived from individuals with latent TB who will mount antigen-specific T cell responses post PPD instillation. This strategy will also decrease variance in Group A via relative oversampling compared to Group B.

Figure 1 outlines the experimental timeline. A baseline PET-CT study of the thoracic cavity will be obtained, and the first bronchoscopy will be performed in the following the week to collect the baseline BAL sample and to instill the PPD as outlined above. Peripheral blood will be collected at the time of each bronchoscopy procedure before the BAL. To examine early immune responses, on approximately day 4 the second PET-CT study will be obtained and the following day a second BAL will be performed, and peripheral blood samples will be collected. BAL will be done first in the control anterior segment of the left upper lobe and then again in the

anterior segment of the right upper lobe. To examine the persistence of this local pulmonary immune response, the next PET-CT image will be obtained on approximately day 20, and the following day 21, repeat blood and BAL samples will be collected as done previously. A repeat IGRA test will be collected on the final visit day of the study to assess for any change in the participant's initial result.

Figure 1. Experimental schematic.

4.2 SCIENTIFIC RATIONALE FOR STUDY DESIGN

Our study design is similar to that of Silver and colleagues in that we are proposing the evaluation of local airway responses in small groups of non-LTBI controls and confirmed LTBI cases. However, we anticipate that our immunological signals will be stronger due to our confirmation of LTBI status using concordant positive TST and positive IGRA tests, and similarly our confirmation of the status of controls without LTBI using concordant for negative TST and negative IGRA tests. In addition, we will be studying responses to antigen challenges in the upper lobes where most humans develop pulmonary TB, rather than the middle lobe as studied by Silver and colleagues. Furthermore, the novelty of our approach will involve the combination of immunological assays after bronchoscopic instillation of antigens directed to specific lung segments and PET-CT scanning to determine the location and kinetics of responses in the draining lymph nodes. The PET-CT scanning component has the potential to provide the first localization of immunological challenge with non-infectious Mtb antigens in humans.

4.3 JUSTIFICATION FOR DOSE

The PPD bronchoscopic instillation dose of 0.5 tuberculin units (10 uL Tubersol® in 10 mL normal saline) was determined by Silver and colleagues in 2003. They demonstrated that the minimally reactive dose of PPD administered through the airways to elicit the development of alveolar inflammation was a challenge dose of 0.5 TU or 1/10th of the standard TST dose (21).

5 STUDY POPULATION

Eligibility will be determined per two screening visits either in person or via a Telehealth visit. Alternatively, if a test result is available from any other NIH protocol within 60 days of enrollment, that test result can also be used for screening purposes.

5.1 INCLUSION CRITERIA

Adults 18-64 years old will be recruited for the two groups (non-LTBI controls vs confirmed LTBI). The lower limit of this age range is based on the need for invasive bronchoscopic

procedures and exposure to radiation, both of which carry more risk at younger ages. In addition, most adults present with post-primary or reactivation TB that most often occurs radiographically in the upper lobes of the lungs, often with cavitation. Conversely, children and rare adults with primary TB have non-cavitary disease in the lower lobes. The higher limit of this age range is based on the known property of immune senescence, i.e., the waning of the strength of immune responses with advancing age.

In order to be eligible to participate in this study, an individual must meet all of the following criteria:

1. Ability of subject to understand and the willingness to sign a written informed consent document.
2. Stated willingness to comply with all study procedures and availability for the duration of the study
3. Male or female, aged 18 – 64 years of age
4. No significant active medical problems. This would include but not limited to any cardiac disorder (e.g. arrhythmia, valvular disease), pulmonary disease (e.g. asthma requiring chronic medications, chronic bronchitis, emphysema, obstructive sleep apnea), kidney disease (e.g. nephritis, nephrosis), rheumatologic disorder (e.g. inflammatory arthritis), endocrine disorder (e.g. diabetes, thyroid disease), liver disease (e.g. hepatitis), gastrointestinal disorder (e.g. inflammatory bowel disease) or infectious disease (e.g. active tuberculosis).
5. For females of reproductive potential: use of highly effective contraception for at least 1 month prior to screening and agreement to use such a method during study participation
6. For males of reproductive potential: use of condoms or other methods to ensure effective contraception with partner and agreement to use such a method during study participation

5.2 EXCLUSION CRITERIA

An individual who meets any of the following criteria will be excluded from participation in this study:

1. Pregnancy as assessed by urinary or plasma HCG or breastfeeding
2. History of clinically significant respiratory dysfunction 3 months prior to participating
 - a. Evidence of new pulmonary infection
 - b. History of any chronic lung infections or chronic lung disease
 - c. History of pulmonary hypertension
 - d. Need for supplemental oxygen administration at rest
3. Current use or inability to suspend use of anticoagulant therapy including platelet inhibitors (e.g. clopidogrel) within 7 days of study bronchoscopy or systemic anticoagulants (e.g. warfarin, enoxaparin, or DOAC) within 14 days of study bronchoscopy
4. Any symptoms consistent with infection including fever, chills, night sweats, or unexplained weight loss
5. A history of a necrotic reaction to a tuberculin skin test, including during screening
6. A history of human immunodeficiency virus (HIV) infection
7. A history of coughing up blood in the last 3 months
8. Cigarette smoking, vaping or recreational drug use within the past 6 months (self-reported)

9. If there is any discrepancy in tuberculin skin test and Interferon Gamma Release Assay test results (i.e. PPD+ but IGRA- or PPD- but IGRA+)
10. Refusal or inability to undergo bronchoscopy, or a history of poor tolerance of a bronchoscopy
11. If undergoing PET-CT imaging during this study places a participant over his/her annual radiation dose limit. Radiation exposure within the previous 12 months of ≥ 2.3 rem
12. BMI > 40
13. Diabetes
14. Known life-threatening allergic reaction to Tuberculin, Lidocaine, Midazolam, Fentanyl or medications of similar classes
15. Presence of any immunosuppressive diseases, including cancers with the exception of non-melanomatous skin cancer.
16. Use of any systemic immunosuppressive medications, including corticosteroids (e.g., prednisone) or biological agents in the last 6 months prior to enrollment
17. Any medical, psychiatric, social condition, occupational reason or other responsibility, in the judgement of the investigator, that is a contraindication to protocol participation or impairs a participant's ability to give informed consent
18. Positive for COVID-19. (with-in 6 months prior to enrollment self-reported and or via PCR)

5.3 INCLUSION OF VULNERABLE PARTICIPANTS

NIH employees and members of their immediate families may participate in this protocol. We will follow the Guidelines, per Policy 404, for the Inclusion of Employees in NIH Research Studies and will give each employee a copy of the “NIH information sheet on Employee Research Participation”.

5.4 LIFESTYLE CONSIDERATIONS

Not applicable.

5.5 SCREEN FAILURES

Screen failures will be defined as participants who consent to participate in the clinical trial but are not subsequently assigned to the study intervention or entered in the study. A minimal set of screen failure information is required to ensure transparent reporting of screen failure participants, to meet the Consolidated Standards of Reporting Trials (CONSORT) publishing requirements and to respond to queries from regulatory authorities. Minimal information includes demography, screen failure details, eligibility criteria, and any serious adverse event (SAE).

Individuals who do not meet the criteria for participation in this trial (screen failure) because of an evidence of active clinical illness, or radiation exposure within the last 12 months of ≥ 2.3 rem, at the time of screening may be rescreened. Subject's may be eligible to be rescreened to participate at a later date if at the time of enrollment they are found to have an active infection, vaccination, and or have been exposed to radiation within the last 12 months of ≥ 2.3 rem, or met criteria, but subsequently not assigned to the study intervention within 60 days.

Abbreviated Title: Tissue-Specific Immune Responses to Tuberculin Purified Protein Derivative (PPD) in the Human Lung **Version Date:** 12/17/2024

If re-screened after 60 days from screening visits, the TST, IGRA, & chest x-ray will not be repeated unless there is a known tuberculosis exposure, including but not limited to travel to an endemic area or direct contact with an individual with known or suspected tuberculosis disease.

The study team may contact the subject at a later date to determine if they would like to continue their participation and complete the screening again.

5.6 STRATEGIES FOR RECRUITMENT AND RETENTION

The study will be listed on the ClinicalTrials.gov, Clinical Center (CC) Search the Studies, and the CC recruitment website. IRB-approved language will be used in all recruitment messaging and the following options for marketing the study may be used:

- ResearchMatch;
- Official NIH social media accounts (including but not limited to Facebook, Twitter, Instagram);
- Community newspapers, magazines, radio, TV ads and/or other appropriate print or electronic media;
- NIH Listservs (GovDelivery, Clinical Fellows, Post Baccalaureate, OPR Study Volunteer), webpages, or other marketing platforms including Clinical Center TVs (CCTV) messaging;
- Physician partnerships to include health specialists;
- Recruitment post cards and flyers printed will be designed for the study and distributed in the community, around the NIH campus, external partnering healthcare centers/offices, and/or any other locations where potential research volunteers may be found.
- Metro train, bus, station ads (Outfront Media company partnership). All messaging will be IRB approved in advance.

A letter to physicians may be used for electronic (and hard copy as appropriate) distribution to local physicians and specialists. All options mentioned in PSA (i.e. ResearchMatch, publications, etc.) may be used for recruitment. Social media posts may be used by the accounts of the Clinical Center and NHLBI, and/or other official NIH accounts. The Healthy Volunteer (HV) listserv will be used for outgoing communications and a regularly updated HV list will be obtained, all through a close partnership with the CC HV office within the Clinical Center Office of Patient Recruitment and Call Center.

5.6.1 Costs

Not applicable

5.6.2 Compensation

Visits to NIH	Amount
Screening Visit #1 – 1hr	\$80
Screening Visit #2 – 1hr	\$80
On-Study Visit #1 (Baseline)– 3hrs	\$120
On-Study Visit #2 (Day 0)– 5hrs	\$120
On-Study Visit #3 (Day 4-5)- 4hrs	\$120
On-Study Visit #4 (Day 5-6)– 5hrs	\$120
On-Study Visit #5 (Day 20-21)– 4hrs	\$120
On-Study Visit #6 (Day 21-22)– 5hrs	\$120
Total for Visits	\$880

Procedures	Amount
Tuberculin skin test (TST) - \$50 x 2 2 nd test may not be needed	\$100
History and Physical	\$20
EKG - \$20 x 4	\$80
Blood work – \$30 x 4	\$120
Research blood work - \$30 x 3	\$90
Screening chest X-ray	\$20
PET-CT - \$250 x 3	\$750
Radioactive tracer - \$80 x 3	\$240
Bronchoscopy - \$300 x 3	\$900
PPD Study drug given with 1 st Bronchoscopy	\$50
Fentanyl and Midazolam IV admin - \$20 x 3	\$60
Escort fee for person staying with vol after bronch \$20 x3	\$60
Total for Procedures	\$2,490
Total (Visits and Procedures) - \$880 +2,490	\$3,370

Recruitment, Selection and Compensation of Research Subjects per Policy 301.

Reimbursement of Travel

Reimbursement for travel will be in accordance with NHLBI travel policy reimbursement for food and lodging will be consistent with NIH and NHLBI guidelines. Car mileage will be reimbursed only if traveling \geq 30 miles away at 0.40 cents per mile. Reimbursement will be provided for long distance $>$ 50 miles for train and bus only.

6 STUDY INTERVENTION

6.1 STUDY INTERVENTIONS(S) ADMINISTRATION

6.1.1 Study Intervention Description

The normal saline control agent (serving as a comparison for PPD administration) for bronchoscopic instillation will be 0.9% sodium chloride solution.

Sterile commercially developed tuberculin PPD will be used for skin-testing and bronchoscopic instillation procedures. Per the Tubersol® Package insert: “Tuberculin Purified Protein Derivative (Mantoux) (PPD) for intradermal tuberculin testing is prepared from a large Master Batch Connaught Tuberculin (CT68) and is a cell-free purified protein fraction obtained from a human strain of *Mycobacterium tuberculosis* grown on a protein-free synthetic medium and inactivated. TUBERSOL is indicated to aid diagnosis of tuberculosis infection in persons at increased risk of developing active disease. It is currently only indicated for intradermal injection.

Endobronchial administration of tuberculin PPD may lead side effects including but not limited to cough, wheezing, bronchospasm, fever, pneumonitis, allergic reaction, or anaphylaxis. The possibility of the occurrence of such side effects will be monitored as detailed below.

This study will be conducted under an Investigational New Drug Application (IND). The IND for Tuberculin Purified Protein Derivative (PPD) TUBERSOL® is 19720.

6.1.2 Dosing and Administration

The PPD bronchoscopic instillation dose of 0.5 tuberculin units (10 uL Tubersol® in 10 mL normal saline) was determined by Silver and colleagues in 2003. They demonstrated that the minimally reactive dose of PPD administered through the airways to elicit the development of alveolar inflammation was a challenge dose of 0.5 TU or 1/10th of the standard tuberculin skin test dose (15).

This instillation will be performed via introduction of a balloon-tipped 5-French pulmonary artery (PA) catheter within the working channel of the bronchoscope, subsequent occlusion of the subsegment of interest, instillation of normal saline control, followed by a saline flush (20). Next, the bronchoscope will be moved to the right lung, where 0.5 tuberculin units (10 microliters of Tubersol®) diluted in 10 cc normal saline will be instilled into the anterior segment of the right upper lobe via a separate 5-French balloon-tipped PA catheter similarly followed by saline flush.

6.1.3 Dose Escalation

Not applicable.

6.1.4 Dose Limiting Toxicity

Not applicable.

6.1.5 Dose Modifications

Not applicable.

6.1.6 Drug Administration

See section 6.1.2

6.2 PREPARATION/HANDLING/STORAGE/ACCOUNTABILITY

6.2.1 Acquisition and Accountability

Sterile commercially developed TUBERSOL® will be used for skin-testing and bronchoscopic instillation procedures. Please refer to the Tubersol® Package insert.

PPD for clinical and in vitro use will be purchased as Tubersol® from Sanofi Pasteur, [name].

6.2.2 Formulation, Appearance, Packaging, and Labeling

As above in section 6.2.1

6.2.3 Product Storage and Stability

Intact vials will be stored in the refrigerator (2°C - 8°C) (36°F - 46°F). The vials will be protected from freezing and light exposure in order to maintain product integrity.

Stability studies have demonstrated that PPD containing the stabilizer of Tween 80 and preservative of phenol are stable for at least 3 years at 4 degrees C, 2 years at room temperature (24 degrees C) and even at 37 degrees C are stable for at least 1 year (27). Per Canadian and U.S. regulations PPD will be stored at 2 to 8 degrees C in their original containers. The reconstituted solution should be stored in the refrigerator (2°C - 8°C). The pharmacy will be notified of when the subject will be ready for the procedure and prepare the syringe at this time. The Syringe will be transferred to the procedural unit per the Pharmacy Drug Preparation Manual Standard of Practice (SOP).

6.2.4 Preparation

Tubersol® contains 0.0005% Tween 80 as a stabilizer and 0.28% phenol as a preservative. In order to administer the experimentally established bronchoscopic instillation dose of 0.5

tuberculin units (TU), 10 ul of the commercial Tubersol preparation will be diluted in 10 ml of saline, creating final concentrations of 0.0000025% Tween 80 of and 0.0014% phenol. To ensure sterility dilutions of PPD will be prepared in a laminar flow hood immediately prior to bronchoscopic instillation using previously unopened vials of Tubersol® and sterile saline. For intradermal injection each standard dose of 5 TU will be administered in the standard volume of 0.1 ml using 26G needles.

6.3 MEASURES TO MINIMIZE BIAS: RANDOMIZATION AND BLINDING

In order to minimize observer and confirmation bias, research specimens collected will be coded so that the principal investigator will be blinded to which group (LTBI vs. non-LTBI) subjects are enrolled, after subject's completion of the schedule of activities but prior to primary data analysis has been completed. Designated AIs and study research nurses will coordinate the process of coding and labeling the samples collected into respective LTBI and non-LTBI groups in a manner that will blind the principal investigator to study group. These specimen code group will only be released to the principal investigator after flow cytometry, and PET-CT data have been collected and undergone primary analysis.

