8.2.3 Correlative Studies for Research/Pharmacokinetic Studies

Special assays or procedures required

Blood will be collected into heparinized Green Top tubes on the day of each bronchoscopy (days 0, 5 and 21). Peripheral Blood Mononuclear Cell (PBMC) and BAL cells will be isolated, stimulated and cell surface molecules, intracellular cytokines and transcription factors will be evaluated via flow cytometry. Peripheral blood and BAL soluble mediators will be analyzed via multiplex kits, mass spectrometry or other techniques.

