9.4 STATISTICAL ANALYSES

9.4.1 General Approach

Statistical analysis will be performed in R version 3.6.1 or later (CRAN.R-Project.org). For the analysis of primary and secondary endpoints, mixed effects models with repeated measure will be used to compare the LTBI and non-LTBI responses after bronchoscopic PPD instillation. For the primary hypothesis, the cell count for Mtb antigen-specific CD4+ and CD8+ T cells will be used as the response variable. Two separate statistical models will be entertained to explain the local pulmonary response and systemic vasculature, respectively. To guard against non-normal responses, a suitable data transformation on the response variable, e.g., log transform, will be performed if the original scale is highly skewed.

In regard to PET CT analysis, calculations for standardized uptake value will be made and normalized for scan differences using OsiriX MD (11). For the secondary hypothesis, the FDG SUV values from the PET CT image, measured at days -7, +4, and +20 days will be used as response in similar mixed effects models to study the group difference in average immunologic responses.

For the exploratory hypotheses, both numerical and graphical summary tools will be used to study the phenotypic and functional analysis of immune cell populations in the airways and circulation of individuals with or without LTBI. Also, descriptive statistics will be used to characterize the production of soluble mediators in BAL fluid and blood.

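### Section 6.3 does not ensure masked measurement: it blinds only the principal investigator, and only after a participant's visits, and states no masking for other flow or PET-CT readers

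*Combined protocol and SAP*

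**What the plan says.** Section 6.3 sets itself the aim of limiting observer and confirmation bias, and does so as follows.

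- **Who is masked.** Specimens are handled so that one role is masked: "research specimens collected will be coded so that the principal investigator will be blinded to which group (LTBI vs. non-LTBI) subjects are enrolled".
- **When.** The masking applies "after subject's completion of the schedule of activities but prior to primary data analysis has been completed".
- **How.** Associate investigators and research nurses are in charge of "coding and labeling the samples collected into respective LTBI and non-LTBI groups"; read to its end, the sentence has the samples sorted "into respective LTBI and non-LTBI groups in a manner that will blind the principal investigator to study group".
- **Until when.** The code goes to the PI only once flow cytometry and PET-CT data have been collected and have had their primary analysis.

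The measurement sections add nothing on masking. Section 8.2.3 has blood and BAL cells stimulated and evaluated by flow cytometry, without saying who sets the gates. Section 9.4.1 says of PET-CT that "calculations for standardized uptake value will be made and normalized for scan differences using OsiriX MD", without naming a reader or saying that the reader is masked.

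**The concern.** Gating rare antigen-specific T cells and placing PET regions both leave room for judgement. The groups are defined by TST and IGRA, not by randomisation, so nothing in the allocation guards against a reader's expectations. The hypotheses in Sections 4.1 and 9.1 are directional: responses mainly in LTBI participants, in the PPD segment, highest early and then waning. A reader who knows the group can, without intending to, produce the predicted contrast. Masked measurement is one of the main safeguards this design has, so the plan should state who is masked and when.

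**Working it through.** The plan states no figure on this point, so there is nothing to reproduce. The check is a reading of the sections side by side, followed by two illustrations.

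**1. Who measures, and whether they are masked**

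| Step | Source | Person named | Masking stated |
|---|---|---|---|
| Coding of specimens | 6.3 | Associate investigators, research nurses | None; they sort by group, so they know it |
| Flow gating | 8.2.3 | None | None beyond the PI's in 6.3 |
| SUV measurement | 9.4.1 | None | None beyond the PI's in 6.3 |
| Coding of PET-CT images | 6.3 | None | Not described; only research specimens are coded |

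If the PI gates or measures, Section 6.3 intends a group blind through primary analysis. If anyone else does, no masking is stated.

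**2. What the PI can know before the blind starts**

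Concordant TST and IGRA results define the groups (Section 4.1). A footnote to the Schedule of Activities (1.3) lets the PI or a designee call for a second TST to confirm a negative result. Section 10.6 has the PI monitor accrual and safety data, and Section 10.8.1 has the PI oversee data entry. Section 8.4.7 has the PI learn of incidental PET-CT findings. With 20 planned completers, a blind that begins after the last visit cannot be relied on to remove that knowledge.

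**3. What is left open to judgement**

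No gating rule is given. The PET regions are described in two ways: lung tissue adjacent to the instillation and its draining nodes in the Synopsis (1.1), but all lung fields and the mediastinal nodes in Section 3.

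**4. Illustration: level of the code**

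Inputs are 13 LTBI and 7 non-LTBI participants (Section 9.2). If specimens carry one of two set-level codes and all 20 are present, the larger set is the LTBI set. With individual codes that carry no group information, the number of ways to choose the 7 controls is

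C(20, 7) = 20! / (7! × 13!) = 77,520.

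**5. Illustration: effect of a group-dependent reading shift**

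Assumptions not in the plan: a two-sided 5% two-sample t-test, no true difference, and reading that moves one group by b standard deviations.

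- Degrees of freedom = 13 + 7 − 2 = 18.
- Standard error = √(1/13 + 1/7) = 0.469 SD.
- Non-centrality λ = b / 0.469.
- Rejection rate = P(|T| > critical value), with T non-central t on 18 degrees of freedom and non-centrality λ.

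| Assumed shift b | λ | False-positive rate |
|---|---|---|
| 0 | 0 | 5.0% |
| 0.25 SD | 0.53 | 8.0% |
| 0.50 SD | 1.07 | 17.3% |

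**The case against.** The best defence is that Section 6.3 does more than a quick reading suggests. The sentence on sorting goes on to say that the labelling is meant to hide group from the PI, and the code is withheld until flow and PET-CT data have had primary analysis. Both points stand. A reader might infer that specimens openly carry their group, or that flow gating and PET measurement have no protection at all. The text supports neither.

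Three other strong readings also fail.

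- **That set size gives the group away.** This needs set-level codes visible to the reader. Section 6.3 does not say whether codes are set-level or individual, and Section 10.3 gives each participant's research data a unique study number. That number is not said to be free of group information, but it weakens the inference. Set sizes also change during accrual, with up to 25 enrolled (Section 4.1) and withdrawn participants replaced (Section 7.2).
- **That sampling on days 0, 5 and 21, before the blind starts, is itself a defect.** Observer bias arises when gates are set and regions drawn, not when blood or BAL is collected. The plan does not date either step. What matters about the late start is what the PI may already know.
- **That the false-positive rate of this trial is 8% or 17%.** Those figures follow from assumed shifts in a t-test. The plan uses repeated-measures mixed models, states no alpha, and describes a hypothesis-generating pilot.

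It can also be said that the specified models compare the two groups, so group is the main thing to mask. That is fair, and it is why masking of segment and visit is asked for only where feasible. It does not answer the main gap, which is that no masked reader is named.

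**Conclusion.** The concern holds as a gap in assurance. Section 6.3 does not secure its own aim: it masks one role, starts when that role may already know TST and IGRA status, codes specimens but not images, and leaves unclear whether codes are individual or by group. Some protection is intended if the PI gates or measures; none is stated for anyone else.

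The size of any resulting bias cannot be derived from the documents. The 8.0% and 17.3% figures show only how sensitive a 13 versus 7 comparison would be under the assumed shifts. They are not estimates for the planned analysis. For a pilot this is a cheap improvement that should be made before measurements are read, since unmasked readings are hard to repair afterwards.

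**What to change.** Amend Section 6.3 as follows.

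1. Give each research specimen and each PET-CT scan an individual random code at collection that carries no group information. The associate investigators and nurses already named hold the key, and key-holders do not gate or measure.
2. Name the roles that gate flow data and measure SUV. Require them to work on coded files, masked to group, until measurements are locked. Mask BAL segment and visit as well where feasible; on PET-CT, visit can be masked but lung side cannot.
3. Fix the gating template and the PET regions in writing before the code is released, and settle which of the two PET descriptions applies.

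Clinical reading of scans and reporting of incidental findings can continue as planned, separate from the research measurement.

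The cost is extra label handling, de-identification of scans, and the work of writing down the gating and region rules. Existing staff can do this, and no participant procedure or sample size changes.
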